6.1.1. Adult Dosing

| | Arm A | Arm B1 | Arm B2 |
|---|---|---|---|
| Intervention | Selpercatinib | Cabozantinib | Vandetanib |
| Adult Dose | 160 mg BID | 140 mg QD | 300 mg QD ^a |
| Authorized as defined by EU Clinical Trial Regulation | Authorized and used according to EU authorization | Authorized and not used according to EU authorization | Authorized and used according to EU authorization |

Abbreviations: BID = twice daily; QD = once daily.

^a Starting dose of vandetanib should be 200 mg in patients with moderate renal impairment (creatinine clearance results between 30 and 50 mL/min). In case vandetanib 100-mg tablets are not available, see Section 6.6.

6.1.2. Adolescent Dosing

| | Arm A | Arm B1 | Arm B2 |
|---|---|---|---|
| Intervention | Selpercatinib | Cabozantinib | Vandetanib |
| Adolescent Dose ^a | 92 mg/m ² BID (not to exceed 160 mg BID) | 40 mg/m ² | See dosing guide |
| Approximate adult equivalent dose | 160 mg BID | 72 mg QD | |
| Authorized as defined by EU Clinical Trial Regulation | Authorized and used according to EU authorization | Authorized and not used according to EU authorization | Authorized and used according to EU authorization |

Abbreviations: BID = twice daily; QD = once daily.

^a Please refer to nomograms below for the exact dosing.

Adolescent patients will have BSA-adjusted dosing as outlined in the tables below. BSA should be determined according to the Mosteller Formula (Mosteller 1987).

Selpercatinib

Selpercatinib dosing will be rounded according to guidelines in the table below. The maximum starting dose will be no higher than 160 mg BID.

Selpercatinib Capsule Dose Rounding (all doses BID)

| BSA (m ²) | Rounded Dose (mg) |
|-----------------------|-------------------|
| <0.76 | 40 mg |
| 0.76 – <1.2 | 80 mg |
| 1.2 – <1.6 | 120 mg |
| ≥1.6 | 160 mg |

Abbreviations: BSA = body surface area.

Vandetanib**Vandetanib Dosing Nomogram for Adolescent Participants**

| BSA (m ²) | Start dose (mg) ^a |
|-----------------------|------------------------------|
| 0.7 - <0.9 | 100 QOD |
| 0.9 - <1.2 | 100 QD |

| BSA (m ²) | Start dose (mg) ^a |
|-----------------------|--|
| 1.2 - <1.6 | 7 day schedule: 100-200-100-200-100-200-100 |
| ≥1.6 | 200 QD |

Abbreviations: BSA = body surface area; QD = once daily; QOD = once every other day.

^a A reduced starting dose of vandetanib should be used in adolescent patients with moderate renal impairment as per the dose reduction table in Section 6.6.

Cabozantinib

Cabozantinib Dosing Nomogram for Adolescent Participants

| BSA (m ²) | Weekly Dose/ Schedule for Initial Dosing |
|-----------------------|--|
| 0.35 – 0.39 | 100 mg = 20 mg M, W, Th, Sat, Sun |
| 0.40 – 0.45 | 120 mg = 20 mg M, T, W, F, Sat, Sun |
| 0.46 – 0.55 | 140 mg = 20 mg QD |
| 0.56 – 0.64 | 160 mg = 40 mg M, W, F, Sun |
| 0.65 – 0.78 | 200 mg = 40 mg M, W, Th, Sat, Sun |
| 0.79 – 0.90 | 240 mg = 40 mg M, T, W, F, Sat, Sun |
| 0.91 – 1.09 | 280 mg = 40 mg QD |
| 1.10 – 1.17 | 300 mg = 60 mg M, W, Th, Sat, Sun |
| 1.18 – 1.36 | 360 mg = 60 mg M, T, W, F, Sat, Sun |
| 1.37 – 1.65 | 420 mg = 60 mg QD |
| 1.66 – 1.85 | 480 mg = 80 mg M, T, W, F, Sat, Sun |
| 1.86 – 2.07 | 560 mg = 80 mg QD |
| ≥ 2.08 | 600 mg = 100 mg M, T, W, F, Sat, Sun |

Abbreviations: BSA = body surface area; QD = once daily.

6.1.3. Exceptional Switch from Vandetanib to Cabozantinib

Participants assigned to the control arm should not switch between control arm treatments. In exceptional situations where vandetanib is not available:

- participants originally assigned to vandetanib may be allowed to switch to cabozantinib during the study.
- physician's choice in the control arm may be limited to cabozantinib only.

If vandetanib is not available and participant fulfills the eligibility criteria listed in Section 6.1.3.1, the participant may be allowed to switch to cabozantinib.

If participant is on reduced dose level of vandetanib due to toxicities, then the corresponding dose level should be considered for starting dose of cabozantinib at switch.

6.1.3.1. Eligibility Criteria for Switching from Vandetanib to Cabozantinib

A switch from vandetanib to cabozantinib will be allowed if study intervention supply is unavailable and after approval by study sponsor.

Conduct safety assessments more frequently during the first 3 cycles of switch treatment. See SoA table, Section 1.3.3.

Eligibility criteria for switching from vandetanib to cabozantinib:

- a) Willing and able to provide written informed consent to switch.
- b) No ongoing AEs impacting hematologic, hepatic, and renal function > G2.
- c) Participant has not previously discontinued due to vandetanib-related AE.
- d) All toxicities attributed to vandetanib have resolved or decreased to Grade 1.
- e) Has discontinued vandetanib for a minimum of 15 days and up to 42 days before treatment with cabozantinib is initiated.
- f) Participant has no disease progression by investigator assessment.

Exceptions to criteria b may be made on a case-by-case basis, following approval from the sponsor.

6.1.4. Packaging and Labeling

Study interventions will be supplied by the sponsor or its designee in accordance with current Good Manufacturing Practice. Study interventions will be labeled as appropriate for country requirements.

6.2. Preparation/Handling/Storage/Accountability

1. The investigator or designee must confirm appropriate temperature conditions have been maintained during transit for all study intervention received, as appropriate, and any discrepancies are reported and resolved before use of the study intervention.
2. Only participants enrolled in the study may receive study intervention and only authorized staff may administer study intervention and/or supply study intervention to participant. All study intervention. must be stored in a secure, environmentally controlled, and monitored (manual or automated) area in accordance with the labeled storage conditions with access limited to the investigator and authorized site staff.
3. The investigator, institution, or the head of the medical institution (where applicable) is responsible for study intervention accountability, reconciliation, and record maintenance (i.e., receipt, reconciliation, and final disposition records).
4. Further guidance and information for the final disposition of unused study interventions are provided in the Pharmacy Manual.
5. Investigators should consult the study drug information provided in the Pharmacy Manual or label for the specific administration information (including warnings, precautions, contraindications, adverse reactions, and dose modifications).

6.3. Measures to Minimize Bias: Randomization and Blinding

This is an open-label study. However, to preserve the integrity of the trial, Lilly will not have unblinded access to aggregate data from the clinical database. An Independent Data Monitoring Committee (IDMC) will evaluate aggregate interim efficacy results to provide recommendations of adaptation at the interim analysis and monitor aggregate safety data during the course of the trial on a regular basis. An external Statistical Analysis Center will conduct interim efficacy and safety analyses and report the results to the IDMC. This practice will ensure that Lilly personnel involved in the day-to-day management and conduct of the trial do not have access to unblinded comparative results, even inadvertently. Additional details are specified in Section 9.5 and separate IDMC and Adaptive Design Charters.

To maintain the trial integrity after the sample size re-estimation, other measures will be taken to avoid disclosure of the interim comparative results:

- Any members of the study team that have access to the adaptation decision will be prespecified and documented. Other Lilly study team members will be shielded as much as possible from the knowledge of adaptive changes.
- The adaptation algorithm and details on the sample size re-estimation will be preserved in an Adaptive Design Charter and stored confidentially in a restricted access area. Only the IDMC, SAC and the Lilly statisticians involved in the adaptive design will have access to the Adaptive Design Charter. No other study team members will have access.
- Investigators and trial participants will not be provided with any details regarding an adaptive decision. For example, if the study will continue (sample size may or may not increase) after the interim efficacy analysis, they will be informed that the targeted patient/event number hasn't been reached rather than being notified of the specific targeted final sample size/number of events. Lilly personnel who have direct interaction with study sites will be appropriately trained on this expectation.

More detailed actions to maintain the trial integrity will be described in the Statistical Analysis Plan.

To minimize investigator bias on the efficacy assessment, the primary endpoint of PFS will be determined based on the assessment of a BICR (see Section 8.1.2). Patients on Arm B will be allowed to cross over to selpercatinib only after progression has been confirmed by the BICR. Details of the BICR will be described in a separate BICR Charter.

6.4. Study Intervention Compliance

Participant compliance with study intervention will be assessed at each visit. Compliance will be assessed by direct questioning, counting returned tablets/capsules, and reviewing patient diaries. Deviation(s) from the prescribed dosage regimen should be recorded in the eCRF.

A participant will be considered noncompliant if he or she takes <75% of the planned doses for assigned study drug in a cycle. A participant will also be considered noncompliant if he or she is judged by the investigator to have intentionally or repeatedly taken $\geq 125\%$ of the planned doses of study drug in a cycle.

6.5. Concomitant Therapy

Any medication or vaccine (including over-the-counter or prescription medicines, vitamins, and/or herbal supplements) that the participant is receiving at the time of enrollment or receives during the study must be recorded along with:

- Reason for use
- Dates of administration including start and end dates.

Patients receiving selpercatinib should avoid concomitant use of CYP2C8-sensitive substrates. If co-administration of a CYP2C8-sensitive substrate cannot be avoided, monitor patients for increased adverse reactions of these drugs.

Caution should be used when co-administration of a P-gp substrate (for example, fexofenadine, loperamide, and digoxin), MATE1 substrate (for example, metformin), or BCRP substrate (for example, sulfasalazine) cannot be avoided in patients receiving selpercatinib. Consider increased monitoring as appropriate. The concurrent use of drugs known to prolong QTc is prohibited (Appendix 7). Drugs with a possible or conditional risk should be avoided if possible. Patients eligible to receive vandetanib should refrain from sun exposure during and up to 4 months after discontinuation of treatment due to possible photosensitivity.

The Lilly medical team should be contacted if there are any questions regarding concomitant or prior therapy. Except as indicated in Section 6.1, patients are not allowed to receive concomitant systemic anti-cancer agents (including immunotherapy agents), hematopoietic growth factors for prophylaxis in C1, drugs with immunosuppressant properties (other than as listed in Section 6.5.4), or any other investigational agents. No new, alternative systemic anticancer therapy is allowed prior to documentation of PD in accordance with protocol specified disease response criteria. No surgical resection of tumor or radiation therapy is permitted except as described in Section 6.5.4.

6.5.1. CYP3A4 Inducers or Inhibitors

For patients receiving selpercatinib: The concomitant use of the strong CYP3A4 inhibitors or inducers should be avoided. See Appendix 7.

If, during the study, patients require initiation of treatment with strong inhibitors or inducers of CYP3A4 for clinical reasons, investigators should consider increased monitoring for the development of new AEs.

Co-administration of selpercatinib with sensitive CYP3A4 substrates may increase their plasma concentrations, which may increase the incidence or severity of adverse reactions for sensitive substrates with narrow therapeutic windows.

For patients receiving cabozantinib: The concomitant use of strong inhibitors or inducers of CYP3A4 should be avoided. If strong CYP3A4 inhibitors cannot be avoided, the cabozantinib dose should be reduced by 20 mg daily; if the CYP3A4 inhibitor is to be discontinued, the regular dose cabozantinib should be resumed 2 to 3 days after discontinuation of the strong inhibitor. If strong CYP3A4 inducers cannot be avoided, the cabozantinib dose should be increased by 20 mg daily; if the CYP3A4 inducer is to be discontinued, resume the regular dose of cabozantinib 2-3 days after discontinuation of the strong inducer. See Appendix 7.

For patients receiving vandetanib: The concomitant use of strong inducers of CYP3A4 should be avoided. See Appendix 7.

6.5.2. Agents That Alter Gastric Acidity (PPIs and H2 blockers)

Since selpercatinib absorption from the gastrointestinal tract may be impacted by stomach acidity, concomitant use of pH-altering agents require additional instructions for patients randomly assigned to treatment arm A.

Avoid concomitant use of a PPI, H2 receptor antagonist, or a locally-acting antacid with selpercatinib. If concomitant use cannot be avoided,

- Take selpercatinib with food (at least 400 calories) when co-administered with a PPI.
- Take selpercatinib 2 hours before or 10 hours after administration of an H2 receptor antagonist.
- Take selpercatinib 2 hours before or 2 hours after administration of a locally-acting antacid.

There are no restrictions on PPI or H2 blocker use for patients randomized to the control arm and who are receiving cabozantinib or vandetanib.

6.5.3. P-gp Substrates or MRP2 Inhibitors

Cabozantinib and Vandetanib may have the potential to increase plasma concentrations of co-administered substrates of P-gp (e.g., fexofenadine, aliskiren, ambrisentan, dabigatran etexilate, digoxin, colchicine, maraviroc, posaconazole, ranolazine, saxagliptin, sitagliptin, talinolol, tolvaptan). Therefore, appropriate clinical (e.g., ECG) and/or laboratory monitoring is recommended for patients receiving concomitant digoxin and such patients may require a lower dose of digoxin. Appropriate clinical monitoring is recommended for patients receiving other P-gp substrates such as dabigatran when given in combination with vandetanib or cabozantinib.

Similarly, the administration of MRP2 inhibitors (e.g., cyclosporine, efavirenz, emtricitabine) may result in increases in cabozantinib plasma concentrations. The use of MRP2 inhibitors should be approached with caution.

6.5.4. Palliative Medicine and Supportive Care

Standard supportive medications may be used in accordance with institutional guidelines and Investigator discretion. The use of granulocyte-colony stimulating factor (G-CSF) is permitted at the discretion of the investigator based on American Society of Clinical Oncology (ASCO) (Smith et al. 2015) and European Society for Medical Oncology (Crawford et al. 2009) guidelines, though may not be used prophylactically in Cycle 1.

If clinically indicated at any time during the study, erythropoietin and packed red blood cell transfusions may be used according to ASCO guidelines (Rizzo et al. 2008). Prophylactic antibiotic treatment should be consistent with ASCO guidelines (Flowers et al. 2013).

Continuation of standard of care medications, including anti-emetic, analgesic, and antidiarrheal medications; electrolyte repletion (e.g., calcium and magnesium) to correct low electrolyte levels; thyroid replacement therapy for hypothyroidism; corticosteroid replacement for adrenalectomy; bisphosphonates, denosumab, and other medications for the treatment of

osteoporosis, prevention of skeletal-related events from bone metastases, and/or hypoparathyroidism; or adjuvant hormonal therapy for patients with a history of prostate cancer (e.g., gonadotropin-releasing hormone [GnRH] or luteinizing hormone-releasing hormone [LHRH] agonists) and breast cancer (e.g., GnRH/LHRH agonists, aromatase inhibitors, selective estrogen receptor modulators [SERMs] or degraders [SERDs]), that the patient has been on for the previous 28 days, are allowed, provided they are not on the list of prohibited concomitant medications (refer to Appendix 7).

Local treatment while receiving study treatment (e.g., palliative radiation therapy or surgery for bone metastases) may be permitted with sponsor approval (which may include confirmation of no PD by BICR); discussion with the Lilly medical team and documentation of approval is required. The disease site under consideration for palliative radiation or surgery must not be a target lesion for response assessment and must not be considered to be clinically or radiographically progressing. Lilly recommends holding selpercatinib for approximately 5 half-lives (approximately 7 days) before and after radiation therapy or surgery. Any concern for disease flare due to a prolonged period off of selpercatinib should be discussed with Lilly, who may permit holding selpercatinib for a shorter period of time.

Any herbal drugs, dietary supplements, etc. known to have anti-tumor activity are not permitted.

In addition, any disease progression requiring other forms of specific antitumor therapy will also necessitate discontinuation from the study.

Appropriate documentation for all forms of premedications, supportive care, and concomitant medications throughout the patient's participation in the trial must be captured on the case report form (CRF).

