- ^b Long-term follow-up begins when the patient completes the 30-day (± 7 days) follow-up visit and ends with the patient's death, upon loss to follow-up, or upon overall study completion, whichever is earlier. No follow-up procedures will be performed for a patient who withdraws informed consent unless he or she has explicitly provided permission and consent.

Note: Baseline/screening assessments and laboratory values drawn within the indicated window of C1D1 may be used for both screening/baseline and C1D1 assessments. There is not a defined interval required from randomization to C1D1.

1.3.3. Exceptional Control Arm Switch Treatment (for participants switching from vandetanib to cabozantinib)

This SoA table reflects the additional or revised procedures for control arm switch. Refer to the SoA table, Section 1.3.2 for complete schedule.

| Exceptional^a Control Arm Switch Treatment (for participants switching from vandetanib to cabozantinib) | | | | | | |
|--|--|-----------------|-----|----|------------------|---|
| | Switch Screening | On-Treatment | | | | |
| | | Cycle = 28 days | | | | |
| | Days relative to start of switch treatment | Cycle X+1 | | | Cycle X+2 – 3 | Instructions |
| | | (±3 days) | | | (±3 days) | |
| ≤42 | D1 | D8 | D15 | D1 | | |
| Procedure | | | | | | |
| Eligibility criteria for control arm switch | X | | | | | See Section 6.1.3.1. Must be confirmed before any switch phase procedures are performed. |
| Informed consent form | X | | | | | ICF must be signed before any switch phase procedures are performed. |
| Vital signs (≥18 years of age) | X | X | X | | See Instructions | Measure vital signs: Perform on Day 1 of Cycles X+2 - X+3: weight, systolic and diastolic blood pressure, pulse rate, and body temperature. After the first 3 cycles of switch treatment, go back to previous frequency, i.e., completion of 1 year of study treatment, obtain every 12 weeks in adult participants only. |
| Vital signs (<18 years of age) | X | X | X | | See instructions | Vital signs will be performed on adolescent participants every 4 weeks starting on Day 1 of Cycle X+2-n and throughout. Height should be measured every 6 months. |
| ECG | X | X | X | | See Instructions | Obtain triplicate local ECGs at screening, on D1 and D8 of Cycle X+1, on Day 1 of Cycles X+2 - X+3. After 3 cycles of switch treatment, go back to previous frequency. It is preferable to obtain ECGs approximately 2 hours after dosing. See Section 8.2.1. |

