After confirmation of eligibility, patients will be randomized in a 2:1 ratio to receive selpercatinib at a starting dose of 160 mg BID (treatment Arm A), cabozantinib at a starting dose of 140 mg QD (treatment Arm B1), or vandetanib at a starting dose of 300 mg QD (treatment Arm B2). Adolescent participants will have weight-based dosing as outlined in Section 6.1. The selection of cabozantinib or vandetanib for each eligible patient is required by the investigator prior to randomization and will be documented in the Interactive Web Response System (Study Schema Section 1.2). This selection is a stratification factor. Up to 2 dose reductions for treatment-related toxicity (see Section 6.6) will be allowed. Dosing will be in oral capsule/tablet form.

Treatment will continue until disease progression, unacceptable toxicity, or death. The treatment decision will be made by investigator assessment (see Section 7). Patients with disease progression per investigator assessment may continue treatment while awaiting BICR confirmation of progression.

Patients discontinuing treatment for any reason other than death, lost to follow-up, or withdrawal of consent will enter the survival follow-up period and be followed every 3 months for the development of radiographic disease progression (if not already occurred) and initiation of subsequent anti-cancer therapies (as allowed by their next treatment regimen [see Section 8.1.1 for additional details]) until death, lost to follow-up, or withdrawal of consent (whichever comes first).

Patients who discontinue treatment and who have radiographic disease progression that is confirmed by BICR and were randomized to cabozantinib or vandetanib may be eligible for crossover to selpercatinib if they meet the eligibility criteria for crossover (see Section 5.2.1). The primary endpoint, progression free survival (PFS) by BICR, will act as a gatekeeper for the key secondary endpoints of treatment failure-free survival (TFFS) by BICR and comparative tolerability, i.e., these key secondary endpoints will be tested conditionally on achieving a statistical significance for the primary endpoint. TFFS will act as a gatekeeper for another key secondary endpoint of comparative tolerability.

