7.1. Discontinuation of Study Intervention

Possible reasons leading to permanent discontinuation of investigational product:

- **Subject Decision**
 - the participant or the participant's designee, for example, parents or legal guardian requests to discontinue investigational product.

If a clinically significant finding is identified after enrollment, the investigator or qualified designee will determine if the participant can continue in the study and if any change in participant management is needed.

In addition, participants will be discontinued from the investigational product in the following circumstances:

- the patient becomes pregnant during the study. See Section 8.3 regarding regulatory reporting requirements on fetal outcome.
- the patient is significantly noncompliant with study procedures and/or treatment
- disease progression (radiographic or clinical progression). Patients with disease progression per investigator assessment may continue treatment while awaiting BICR confirmation of progression. Exceptions for continuing study treatment beyond suspected radiographic progression may be made on a case-by-case basis for patients who are believed to be clinically benefiting from study treatment, and the investigator and Lilly medical team agree that continuing study treatment is in the patient's best interest. Expectations for required study procedures and data collection for each patient will be made at the time of approval.
- the patient experiences unacceptable toxicity from study treatment
- the patient, for any reason, requires treatment with another therapeutic agent that has been demonstrated to be effective for treatment of the study indication. Discontinuation from study treatment will occur prior to introduction of the new agent
- the investigator decides that the patient should be discontinued from study treatment.

Participants discontinuing from the investigational product for any reason should complete AE and other follow-up procedures, including imaging assessments, per Section 1.3 (Schedule of Activities), Section 8.3 (Adverse Events and Serious Adverse Events), and Section 8.2 (Safety Assessments) of the protocol.

Participants assigned to treatment Arm B who experience progression may cross-over to selpercatinib after meeting criteria in Section 5.2.1 and comply with procedures noted in Section 1.3.

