7.2. Participant Discontinuation/Withdrawal from the Study

Participants will be discontinued in the following circumstances:

- enrollment in any other clinical study involving an investigational product or enrollment in any other type of medical research judged not to be scientifically or medically compatible with this study
- participation in the study needs to be stopped for medical, safety, regulatory, or other reasons consistent with applicable laws, regulations, and Good Clinical Practices (GCP)
- subject decision
 - the participant or the patient's designee, for example, parents or legal guardian] requests to be withdrawn from the study.

Participants discontinuing from the study prematurely for any reason should complete AE and other safety follow-up per Section 1.3 (Schedule of Activities), Section 8.3 (Adverse Events and Serious Adverse Events), and Section 8.2 (Safety Assessments) of this protocol.

Participants discontinuing from study procedures may continue to be followed for survival, as long as they have not withdrawn consent for follow-up. If an in-person visit is not possible, survival status may be obtained by the site by contacting the patient directly via phone.

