For each modality, IV and oral contrast should be utilized (chest CT does not require contrast) unless there is a clear contraindication (e.g., decreased renal function or allergy that cannot be addressed with standard prophylactic treatments). Post-baseline imaging should be performed every 8 weeks (± 7 days) for 24 weeks and every 12 weeks (± 7 days) thereafter, including imaging of the neck, chest, abdomen, and pelvis, and any other known sites of disease, using the same modality(ies) as used for baseline imaging obtained during the screening period until PD, withdrawal of consent, or death. For the purpose of determining progression for eligibility, a change in modality *may* be acceptable if clear progression can be confirmed by central review, especially when a less sensitive modality was used for the second scan (e.g., liver metastases present on CT abdomen occurring after a previously normal MRI abdomen). Additional studies can also be performed at any time as clinically indicated. Please see the Site Imaging Manual for guidelines on how the various imaging studies should be performed and transmitted for central review.

For patients who progress on study treatment and begin a different anti-cancer therapy (including patients who are initially assigned to the control arm and crossover to receive seliperatinib), PFS2 will be collected. It is recommended to maintain the study imaging schedule in patients who have discontinued treatment; that is, to continue imaging every 8 weeks for the first 24 weeks of the next therapy, then every 12 weeks, as much as allowed according to the patient's new treatment standard of care. These images will be collected centrally and the overall tumor assessment should be entered into the CRF.

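### Protocol 6.5.4 and 7.2 take patients off study at new antitumor therapy or entry to another trial, contradicting the planned PFS2 and post-therapy follow-up

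*Protocol*

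**What the plan says.** Two protocol rules remove patients from the study.

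- Section 6.5.4, on supportive care, states that "any disease progression requiring other forms of specific antitumor therapy will also necessitate discontinuation from the study".
- Section 7.2, on leaving the study, lists "enrollment in any other clinical study involving an investigational product" among the reasons a participant will be discontinued. It does not limit this to patients still on study treatment. It then adds that patients who discontinue study procedures "may continue to be followed for survival, as long as they have not withdrawn consent for follow-up". PFS2 is not named.

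Other sections keep the same patients in.

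- Section 7.1, for a patient who needs another effective agent: "Discontinuation from study treatment will occur prior to introduction of the new agent". Only study treatment stops.
- Section 4.1: "Patients discontinuing treatment for any reason other than death, lost to follow-up, or withdrawal of consent will enter the survival follow-up period". That follow-up is 3-monthly and records radiographic progression and subsequent therapies.
- Section 8.1.1 sends all patients to long-term follow-up and collects PFS2 "For patients who progress on study treatment and begin a different anti-cancer therapy".
- Schedule of Activities, Section 1.3.2: survival and PFS2 assessment runs to the final OS analysis. Footnote b ends long-term follow-up at death, "upon loss to follow-up, or upon overall study completion, whichever is earlier", and allows no procedures after withdrawal of consent. Neither new therapy nor another trial is listed.

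**The concern.** PFS2 and OS are secondary endpoints, and PFS2 exists only if patients are followed through their next line. The patients in whom Section 8.1.1 collects PFS2 are those whom Section 6.5.4 takes off study. Under SAP Table JZJB.10, a patient with neither progression nor death on the next line is censored at the later of the last progression-free assessment and the start of that line. Removal at that point therefore yields almost no PFS2 information.

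Two sensitivity analyses are also exposed. PFS SA2 (SAP Table JZJB.4) and TFFS SA5 (Table JZJB.8) ignore new systemic therapy and count BICR progression or death after it starts. Both need follow-up that a literal reading of 6.5.4 would end.

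Patients who move to another therapy or trial are not a random subset, so censoring them at that point could be informative.

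**Working it through.** **1. Passages compared by type of patient**

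- *Progresses and needs another agent.* Off study under 6.5.4. Under 7.1, 4.1 and 8.1.1, off treatment only, with next therapy, PFS2 and survival still recorded.
- *Has stopped study treatment and later joins another trial.* Discontinued from the study under 7.2. Still in long-term follow-up under footnote b and 4.1.
- *Progresses per investigator but not per BICR, and stops treatment.* Section 8.1.2 continues imaging until BICR verifies progression, death, withdrawal of consent or study completion. Section 6.5.4 would end it if other therapy is needed.

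The protocol separates stopping treatment (7.1) from leaving the study (7.2), so the word study in 6.5.4 cannot simply be read as treatment.

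**2. The plan's own figures**

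- PFS (Protocol 9.2; HR 0.5, one-sided 2.5%, 2:1): events = (1.960 + 0.842)² / [(2/9)(ln 0.5)²] = 73.5, so 74; power at 74 events is 80.3%. Reproduced.
- OS (Protocol 9.4.3.2.3; 125 deaths, HR 0.7): Φ(√(125 × 2/9) × |ln 0.7|) = Φ(1.88) = 97.0% at 2:1, and 97.7% with the 1:1 formula. The stated figure is about 98%.

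**3. Could the loss differ by arm?**

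Section 8.1.2 gives an in-study next line to Arm B only. Inputs from Protocol 9.2 and 4.1: median PFS 50 months (A) and 25 months (B), 250 patients at 2:1 (166.7 and 83.3). Assumptions not in the documents: exponential PFS, uniform accrual over 36 months (24 and 48 also tried), and every patient with a PFS event who does not cross over leaves. PFS events include deaths, so the counts are upper bounds.

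For accrual period a and calendar time T, P(event) = 1 − [exp(−λ(T − a)) − exp(−λT)] / (λa), with λ = ln 2 / median. With a = 36, 74 events are reached at T = 38.5 months: P = 0.239 in Arm A (39.9 events) and 0.409 in Arm B (34.1 events).

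| Share of Arm B events that cross over (assumed) | Arm A leaving | Arm B leaving |
|---|---|---|
| 0% | 40 (24%) | 34 (41%) |
| 25% | 40 (24%) | 26 (31%) |
| 50% | 40 (24%) | 17 (20%) |
| 75% | 40 (24%) | 9 (10%) |

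Break-even for equal proportions: c = 1 − P(A)/P(B) = 1 − 0.239/0.409 ≈ 0.42. Over 24 to 48 months' accrual it is 0.40 to 0.43; at the 72-month cap, 0.30 to 0.33.

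**4. OS if deaths go unobserved**

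About 60% of deaths fall in Arm A (medians 100 and 70 months from Protocol 9.4.3.2.3; 36 months' accrual, 72-month cap). Loss rates are assumed.

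| Deaths lost, A / B | Observed of 125 | P(observed HR < 1) |
|---|---|---|
| 10% / 5% | 115 | 96.4% |
| 25% / 10% | 101 | 95.5% |
| 50% / 20% | 77 | 93.1% |

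These figures leave out any bias from informative censoring.

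**The case against.** The case that this matters little has four parts.

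- **One sentence against many.** Section 6.5.4 concerns care during treatment, while 7.1 addresses the same event and stops treatment only. Section 6.7 tells investigators to follow the Schedule of Activities until notified of study end, and Section 8 requires adherence to it. Most sites would probably keep following patients. This stands as a reason not to assume wholesale loss. It does not remove the conflict, and 7.2 is the governing section for leaving the study.
- **OS is protected.** Section 7.2 says "Participants discontinuing from study procedures may continue to be followed for survival". Section 7.3, under lost to follow-up, has sites or a third party seek vital status for all randomized participants. This largely stands: OS follow-up is left optional, not ended.
- **The confirmatory results barely depend on it.** SAP Tables JZJB.3 and JZJB.7 already censor at new systemic therapy, and PFS2 is outside the alpha-controlled sequence. This stands.
- **Progression data from another trial depend on that trial's schedule.** Sections 4.1 and 8.1.1 already say so. This stands and limits what a fix can achieve.

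A reader might also infer that Arm A will lose more patients because it has no in-study crossover. By count it would at any crossover share, but 2:1 allocation alone produces that. By proportion, Arm B loses more when crossover is low (41% against 24% at none). The documents give no crossover rate, and Section 5.2.1 makes crossover conditional. Sections 7.1 and 8.1.2 also let some patients continue study treatment beyond progression.

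**Conclusion.** The contradiction holds and rests on wording alone. Sections 6.5.4 and 7.2 end study participation for patients whom 4.1, 7.1, 8.1.1 and the Schedule of Activities keep in follow-up. Applied literally, they cost PFS2 data and the progression data after new therapy used in PFS SA2 and TFFS SA5. The main PFS analysis is not materially affected. OS is affected only where optional survival follow-up and vital-status collection are not carried out; under the assumed losses the plan's probability falls from 97.0% to between 96.4% and 93.1%, before any bias.

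A differential loss is possible but not established. Arm A's proportion exceeds Arm B's only if more than about 40% to 43% of Arm B events lead to crossover at 74 PFS events, or 30% to 33% at the cap. That rests on the assumed accrual and on every non-crossover event leaving. The documents also do not support reading the text as meaning that all progressed patients will be lost, or that OS follow-up stops.

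**What to change.** Reconcile Sections 6.5.4 and 7.2 with 4.1, 7.1, 8.1.1 and the Schedule of Activities in Section 1.3.2. State in one place that starting another anticancer therapy, or joining another study after study treatment has stopped, does not end long-term follow-up. Next therapy, progression on it (as far as the next regimen allows) and survival are then collected unless consent is withdrawn. This concerns data collection only and leaves the rules on stopping treatment as they are.

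The cost is small: a wording change in the next amendment and a note to sites. The V802-8XX contacts are already scheduled, and no design figure changes (74 PFS events, 125 OS events). The drawbacks are some extra data entry and, for patients in another trial, progression data limited by that trial's schedule.
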